## **SCREENING**

### **PHASE 1 OF SCREENING**

Phase 1 of screening is conducted via telephone by a CITI trained research assistant to determine if participants meet the initial inclusion and exclusion criteria listed below. The results are entered in REDCap, an online secure database. All information entered in Redcap is de-identified using a screen ID. Any identifying information is entered in a password-protected Excel document on our server.

Inclusion and Exclusion Criteria: Participants are screened at 20-29 weeks gestation

Inclusion:

1. Healthy pregnant women between 18-45 years old [phone screen, self report]:
2. A healthy, singleton pregnancy [phone screen, self report]
3. Fluent English speaker [phone screen, self report]
4. Receiving standard prenatal care [phone screen, self report]
5. A score of 19 or greater on the Predictive Index of Postnatal Depression (PIPD), indicating risk for developing postpartum depression; or score of 7 or greater on the Edinburgh Postnatal Depression Scale (EPDS). [phone screen, assessment administered by trained staff]

Exclusion:

1. Multi-fetal pregnancy [phone screen, self report]
2. Illicit drug use, alcohol use during pregnancy [phone screen, self report]
3. Acute medical illness or significant pregnancy complication [phone screen, self report]
4. Currently in weekly, individual psychotherapy, including psychopharmacology [phone screen, self report]
5. Psychotic d/o; Bipolar I; Major Depressive Disorder [phone screen, MINI assessment and clinical interview administered by trained clinicians] (Determined in Phase 2 of Screening)

If eligible based on the initial phone screen, participants are asked to participate in a follow-up screening session, either by telephone or via HIPAA compliant video call to assess the final IRB approved exclusion Criteria (which are determined by the clinical interview and MINI assessment, which is administered by a licensed clinician or an unlicensed clinician under licensed supervision.

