#### **Baseline Assessment (20-29 weeks gestation):**

A trained research worker will administer the Hamilton Anxiety Scale (HAM-A) and Hamilton Depression Scale (HAM-D) to the participant.

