**Aim 3. Identify some of the pathways by which PREPP positively affects the dyad.** We hypothesize that PREPP-associated: (A) Lower depression scores postpartum will be mediated by concurrent and/or temporally earlier maternal reports of less infant fuss/cry behavior and higher parenting competence; (B) Less infant fuss/cry behavior will be mediated by fewer concurrent and/or temporally earlier negative infant attributions and higher concurrent observed maternal sensitivity; (C) More positive perceptions and objective assessments of maternal

postpartum sleep efficiency will be mediated by greater infant left frontal EEG power reflecting sleep spindle activity and associated longer average durations of infant nocturnal sleep per maternal report and actigraphy.

**Analysis for Aim 3:** Structural equation models will be used to test multiple-mediation. The mediation and Lavaan R packages will be used for this modeling as it can accommodate both continuous and ordered categorical (including dichotomous) variables. Indirect effects (i.e. combined mediational pathways) will be tested using the bootstrapping with 10000 resampling. Specifically for Aim 3A, we will test whether the effect of PREPP on maternal depressive symptoms at week 16 is mediated by infant fuss/cry behavior and higher parenting competence assessed at 6 and 16 weeks after delivery. A model without inclusion of week 16 mediators will also be considered (due to the contemporaneity of week 16 with the outcome). For Aim 3B, the primary outcome is infant fuss/cry behavior at week 16 and mediators are the maternal reports of negative infant attribution assessed at 6 and 16 weeks after delivery and maternal sensitivity at week 16 after delivery. Because of the concurrently observed mediators and outcomes, alternative mediational pathways will be evaluated and compared. For Aim 3C, a mediation model with EEG power at week 6 and avg. infant sleep (actigraphy) quality will be assessed as mediators of the treatment effect on maternal sleep at week 16, controlling for EEG power at birth as a covariate.

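### Aim 3A does not adjust its mediator-to-depression paths for depression before randomisation, so if PREPP moves a mediator, mediation can be declared too often

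*Combined protocol and SAP*

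**What the plan says.** The hypothesis for Aim 3A is that lower postpartum depression scores are mediated by "concurrent and/or temporally earlier maternal reports of less infant fuss/cry behavior and higher parenting competence". The analysis text tests whether "the effect of PREPP on maternal depressive symptoms at week 16 is mediated by infant fuss/cry behavior" and competence. Week-16 maternal depressive symptoms are thus the outcome, "mediated by infant fuss/cry behavior and higher parenting competence assessed at 6 and 16 weeks after delivery". The models are structural equation models, and indirect effects "will be tested using the bootstrapping with 10000 resampling". No covariate is listed for Aim 3A. Its one stated variant is: "A model without inclusion of week 16 mediators will also be considered", because those mediators are measured at the same time as the outcome.

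Baseline adjustment is specified elsewhere in the Statistical Analysis Plan:

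- Aim 1A adjusts EPDS for the screening score.
- Aim 2A puts pregnancy values into its mixed models.
- Aim 3C is fitted "controlling for EEG power at birth as a covariate".
- The general rule under Overall adds covariates when the arms are found to be imbalanced. Its examples are age, BMI, birth order and infant sex. The exploratory covariates listed after it are biological. Depression appears in neither list.

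Depression is measured before assignment. At the Baseline Assessment (20-29 weeks) a research worker "will administer the Hamilton Anxiety Scale (HAM-A) and Hamilton Depression Scale (HAM-D) to the participant". EPDS is scored at screening, where entry is by a risk-index score "or score of 7 or greater on the Edinburgh Postnatal Depression Scale (EPDS"). Randomisation follows at Prenatal Session 1 (28-32 weeks).

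**The concern.** In a mediation model randomisation makes the treatment-to-mediator path unconfounded. It does nothing for the mediator-to-outcome path, which is an observational association within a trial. A woman with more symptoms before assignment may later report more infant crying, feel less competent, and score higher for depression at week 16. The mediator and outcome then correlate within each arm even if the mediator has no effect.

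The existing provisions do not reach this. Confounding of this kind is present when the arms are perfectly balanced, so a rule triggered by imbalance is the wrong safeguard. Dropping the week-16 mediators fixes a timing problem, but antenatal depression precedes the week-6 mediators as well.

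Aim 3 exists to say how PREPP works. If PREPP does shift reported crying or competence, the unadjusted model can credit that shift with a reduction in depression it did not cause.

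**Working it through.** **Inputs from the documents (Power analysis).** N = 142 completers of 214, with 33% attrition; both paths d = 0.54, r = 0.26; stated power above 80%; within-subject correlation 0.2, given for Aim 1.

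**Assumptions.** Two-sided alpha 0.05, since none is stated for Aim 3; one mediator; linear models; true mediator-to-outcome effect zero. Let g and h be the standardised effects of pre-randomisation depression on the mediator and on week-16 depression. The documents give neither, so both are varied.

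**Step 1: the plan's own figures.**

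- 214 × 2/3 = 142.7, and 214 × 0.67 = 143.4, so 142 is reproduced to rounding.
- r = 0.54/√(0.54² + 4) = 0.261.
- Power of the treatment-to-mediator path: Φ(atanh(0.26) × √139 − 1.96) = 0.880. Mediator-to-outcome path, one degree of freedom fewer: 0.878. Joint: 0.880 × 0.878 = 0.773.
- Simulation gives 78.5% for the joint test, 78.2% for the percentile bootstrap and 84.9% for the bias-corrected bootstrap. The stated power is thus reproduced with a bias-corrected interval and narrowly missed otherwise. It presumes no mediator-outcome confounding.

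**Step 2: false mediation without adjustment.** Given treatment, take the mediator as g × U plus noise and the outcome as h × U plus noise, each with unit variance, where U is standardised baseline depression. Their partial correlation given treatment is g × h. Then

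- z = atanh(gh) × √(142 − 4)
- P(mediator-to-outcome path significant) = Φ(z − 1.96) + Φ(−z − 1.96)
- P(mediation declared) = 0.880 × that probability.

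Example with g = 0.3, h = 0.4: gh = 0.12; z = 0.1206 × 11.747 = 1.416; Φ(−0.544) + Φ(−3.376) = 0.294; 0.880 × 0.294 = 0.259.

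| g (mediator) | h (week 16) | Formula | Simulation, unadjusted | Simulation, adjusted |
|---|---|---|---|---|
| 0.2 | 0.2 | 6.7% | 6.4 to 8% | 4.6% |
| 0.3 | 0.2 | 9.6% | 9.2% | about 5% |
| 0.4 | 0.2 | 13.7% | 13.9 to 15% | about 5% |
| 0.2 | 0.3 | 9.6% | 9 to 10.5% | 4.1 to 4.9% |
| 0.3 | 0.4 | 25.9% | 26.4 to 28.2% | 4.0 to 4.6% |
| 0.3 | 0.5 | 37.6% | 37.9 to 40.2% | 4.3 to 4.5% |
| 0.4 | 0.5 | 58.4% | 61 to 63% | 4.5 to 4.8% |

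Ranges come from separate simulations that scaled the mediator slightly differently.

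**Step 3: what changes the answer.**

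- *Treatment effect on the mediator.* With none, unadjusted error was at most 4.6% (joint test) and 5.7% (bias-corrected bootstrap). With r = 0.10, the (0.3, 0.4) cell falls to 6.5%.
- *Sample size.* The plan says the mediation models will use all 214. More data makes the false path easier to detect: (0.3, 0.4) rises to 43%.
- *Bootstrap.* At g = h = 0.4 and N = 142, unadjusted error is 43% (percentile) and 53% (bias-corrected). Adjusted error is 4.3% and 8.0%, so the bias-corrected interval is somewhat liberal even after adjustment.
- *Several mediators.* With four mediators (assumed residual correlation 0.3) and a combined indirect effect, the (0.3, 0.4) and (0.3, 0.5) cells give 35% and 53% unadjusted, 2 to 3% adjusted.
- *Imperfect baseline measure.* With assumed reliability 0.8, adjusted error is 5 to 8%.

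**The case against.** The strongest reply concerns size. The one persistence figure in the documents is the within-subject correlation of 0.2, for assessments weeks apart in pregnancy. The gap from 20-29 weeks' gestation to 16 weeks postpartum is longer and spans delivery. At h = 0.2 the inflation is modest. In addition, screening excludes major depressive disorder and women in weekly psychotherapy, which trims the upper end of antenatal depression and would tend to weaken the correlations involved. Both points stand. A reader might infer that antenatal depression varies widely in this sample, or that a false-mediation rate near 30% or above is to be expected. The documents give no distribution and no such correlations, so neither follows. The 0.2 is itself a planning value for another aim, so it anchors the lower scenario without settling the matter.

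A second reply is that false mediation needs PREPP to move the mediator. That also stands. A reader might infer that persistence of antenatal symptoms is enough on its own; Step 3 shows otherwise. The condition is nonetheless the one the plan expects: Aim 2B hypothesises less fuss/cry, and the power section assumes r = 0.26.

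Third, adjusted error near 5% is partly built in, because baseline depression is the only confounder simulated. Mood arising after randomisation can colour week-6 reports and persist to week 16, and baseline scores will not remove that.

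Fourth, no simulation covers Aim 3B. One of its mediators is observed maternal sensitivity, not a maternal report, and the plan already promises to compare alternative pathways there.

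Finally, Aim 3 is mechanistic, and the five primary outcomes belong to Aims 1 and 2. A reader might infer a threat to the efficacy conclusion; there is none from this source. Nor does the plan forbid adjustment. It is silent, which leaves the choice to be made after the data are seen.

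**Conclusion.** The concern holds in a conditional form. The Aim 3A model as written leaves its non-randomised paths open to confounding by depression before randomisation, and no other provision closes the gap.

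If PREPP moves the mediator by r = 0.26 and the mediator truly does nothing, mediation is declared in about 7 to 15% of trials at a baseline-to-week-16 effect of 0.2 and baseline-to-mediator effects of 0.2 to 0.4. At 0.3 on the mediator and 0.4 to 0.5 on the outcome it is about 27 to 39%, and at 0.4 and 0.5 about 60%. Adjustment brings it to about 5%.

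The existence of the gap is certain from the text. Its size is not: it rests on effects the documents do not give, an assumed alpha of 0.05, N = 142 and a single mediator. Where PREPP does not change the mediator, error stays at about 5% or below.

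**What to change.** In the analysis text for Aim 3:

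1. Include screening EPDS and baseline HRSD as covariates in every mediator equation and in the outcome equation of Aim 3A. Name the pre-assignment values explicitly, because both scales are repeated at Prenatal Session 1, where randomisation takes place.
2. Do the same in Aim 3B where mediator and outcome are both mother-reported (negative attributions and fuss/cry).
3. State that this does not remove confounding that arises after randomisation, and report a sensitivity analysis showing how strong unmeasured mediator-outcome confounding would have to be to explain the indirect effect.

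The cost is SAP wording and two degrees of freedom per equation. Both scores are already scheduled before assignment, so no new data are needed.

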### Baby Day Diaries

At 6 and 16 weeks postpartum, mothers are asked to complete four consecutive days of 24-hour diaries describing infant and parental behavior (the Baby Day Diary). The diaries allow for notation of infant cry, fuss, and awake-content, feeding and sleeping activity. Caregiving behavior is also noted, including; changing, bathing, dressing, holding/carrying and playing/talking behaviors as well as their own sleep periods. Baby diaries take about 30 minutes to complete.

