**Analysis for Aim 1B:** Two ActiGraph-derived measures, total sleep time (TSTact) and sleep efficiency (SEact), will serve as outcomes in separate mixed-effects models with fixed effects for time and day (within the ActiGraph epoch) and subject-specific random intercepts, assuming an AR(1) correlation structure. We will assess whether adjustment for weekday/weekend is warranted. Subject-specific means of these measures will be used as predictors of their subjective

counterparts (TSTact, SEact) in additional mixed models testing for treatment group differences in the association between objective and subjective sleep measures. Moderation by trauma history and attachment will be explored.

**Aim 2. Determine the maintenance of improved maternal mood and differences in infant behavior.** We hypothesize that PREPP will be associated with: (A) Lower rates of PPD and distress, including poor sleep efficiency, assessed by interviewer-rated and self-report questionnaires as well as sleep actigraphy. (B) Less infant fuss/cry behavior and longer nocturnal sleep bouts based on maternal report and actigraphy.

**Analysis for Aim 2A:** Separate linear mixed-effects models will be used for each maternal mood outcome (PHQ-9, HRSD, EPDS, HRSA, PSQI) and ActiGraph-derived sleep measures. Models will include Treatment, Time (6, 12, and 16 weeks postpartum), and their interaction, with baseline (pregnancy) values as covariates. Subject-specific random intercepts will be included. The primary parameter of interest is the Treatment  $\times$  Time interaction; if non-significant, the main effect of Treatment will be tested. PPD diagnosis will be modeled using mixed-effects logistic regression with analogous fixed effects.

For infant outcomes (6 and 16 weeks), linear mixed-effects models will assess Treatment effects without Time  $\times$  Treatment interaction. Sleep data will be processed as in Aim 1B. Covariates include time-varying factors such as weaning, solid food introduction, maternal return to work, and social support. Moderators (infant sex, trauma history, attachment) will also be assessed.

**Analysis for Aim 2B:** Infant sleep and cry behavior at 6 and 16 weeks will be compared using mixed-effects models with Treatment, Time, and their interaction as fixed effects. Covariates and secondary analyses will be same as those in Aim 2A.

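### Aim 3B tests 6-week attributions as a mediator of week-16 infant crying without 6-week crying in the model, so stable fussiness can pass for an attribution pathway if PREPP shifts 6-week attributions

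*Combined protocol and SAP*

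**What the plan says.** The Aim 3 hypotheses allow mediators measured at the same time as the outcome or earlier. For Aim 3B, the Analysis for Aim 3 states that "the primary outcome is infant fuss/cry behavior at week 16 and mediators are the maternal reports of negative infant attribution". It gives the timing of the mediators as "negative infant attribution assessed at 6 and 16 weeks after delivery and maternal sensitivity at week 16 after delivery". No 6-week fuss/cry term is listed. The one safeguard specific to Aim 3B reads "Because of the concurrently observed mediators and outcomes, alternative mediational pathways will be evaluated and compared"; the alternative pathways are not named.

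Six-week crying is available. Under Baby Day Diaries, "At 6 and 16 weeks postpartum, mothers are asked to complete four consecutive days of 24-hour diaries", which record cry and fuss. Aim 2B already uses the measure: "Infant sleep and cry behavior at 6 and 16 weeks will be compared using mixed-effects models".

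The two sister models carry protections that Aim 3B lacks. For Aim 3A, "A model without inclusion of week 16 mediators will also be considered". Aim 3C is fitted "controlling for EEG power at birth as a covariate", that is, with an earlier value of its week-6 EEG mediator. The general covariate text covers baseline imbalance and biological factors, and the Aim 2 covariates are weaning, solid food, return to work and social support. Neither brings earlier crying into Aim 3B.

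**The concern.** Randomisation protects the path from treatment to attributions. It does not protect the path from attributions to crying. Six-week crying is a plausible common cause of both ends of that second path: it can shape how the mother reads her infant at 6 weeks, and it tends to persist to 16 weeks. With it left out, the coefficient of 6-week attributions on week-16 crying is non-zero even if attributions do nothing.

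The lag from week 6 to week 16 is what gives the temporally earlier hypothesis its force, and a reader will take it as evidence of direction. At stake is a claim about mechanism: that PREPP works on infant crying by changing maternal attributions, when the link may be only infant fussiness carried forward.

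**Working it through.** **Inputs from the Power analysis paragraph.** N = 214 (107 per group), 33% attrition, 142 completers, and d = 0.54 (r = 0.26) on both mediation paths. These agree with each other: r = d/√(d² + 4) = 0.54/√4.2916 = 0.261, and 107 × 0.67 = 71.7, so 71 per arm and 142 in all. No alpha is stated for Aim 3; two-sided 0.05 is assumed here.

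**The plan's own figure.** The plan claims more than 80% power for mediation. The treatment path (d = 0.54, 71 per arm) has power 0.89. The mediator path (r = 0.26, Fisher z = 0.266 × √139 = 3.14) has power 0.88. Their product is 0.785. In simulation the percentile bootstrap gives 77–78% and the bias-corrected bootstrap 83–84%. The plan says only that indirect effects "will be tested using the bootstrapping with 10000 resampling", without the interval type, so the claim reproduces with the bias-corrected interval only. The present point does not depend on it.

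**Assumptions.** The documents give neither the correlation of attributions with crying at 6 weeks (λ) nor the correlation of crying at 6 and 16 weeks (s). Both are varied. PREPP lowers 6-week attributions by d = 0.54 and has no effect on crying. Attributions have no effect on week-16 crying, so every detected pathway is false.

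**Closed form, 6-week attribution as sole mediator.** The induced correlation of 6-week attributions with week-16 crying is λ × s. The chance that this path is significant is about Φ(atanh(λs)·√139 − 1.96). Multiplying by 0.89 for the treatment path approximates the rate of false mediation. The last two columns are simulated (joint significance of both paths).

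| λ = s | λs | path significant | × 0.89 | simulated, without 6-week crying | simulated, with it |
|---|---|---|---|---|---|
| 0.3 | 0.09 | 0.19 | 0.17 | 16–18% | 4–5% |
| 0.4 | 0.16 | 0.48 | 0.43 | 40–44% | 4–5% |
| 0.5 | 0.25 | 0.85 | 0.76 | 74–78% | 4–5% |

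The simulated ranges are the spread over repeated runs of 2,000 to 4,000 trials per cell. With a percentile bootstrap and s taken up to 0.7, the rate is 18–85% without 6-week crying and 5–7% with it (400 trials per cell).

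**Dependence on what PREPP does** (percentile bootstrap, same sole-mediator model, λ of 0.3 or 0.5, s from 0.3 to 0.7):
- PREPP moves neither 6-week attributions nor crying: 1–7% without 6-week crying, 0–1% with it. By joint significance at λ = s = 0.3 to 0.5, the unadjusted rate is 1–4%.
- PREPP lowers 6-week crying by d = 0.54 and attributions merely follow: 2–36% without, 0–1% with.
- PREPP lowers both by d = 0.3: 10–79% without, 2–5% with.

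**The model as listed, with week-16 attributions kept.** Suppose week-16 attributions follow 6-week attributions and also respond to week-16 crying. The serial path (PREPP to 6-week to 16-week attributions to crying) is then falsely significant in 87–88% of trials without 6-week crying and 80–86% with it. With 6-week crying added, the direct 6-week path is falsely significant in 18–24%, with its sign reversed. Other assumed coefficients give 24–88% for that direct path. Adding the covariate therefore does not cure this model.

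**The case against.** **The sizes come from a reduced model.** This stands. The 18% to 75–78% applies to 6-week attribution as sole mediator, and the plan states a reduced model for Aim 3A, not for Aim 3B. For the combined indirect effect with both attribution waves in the model, false mediation was 10–14% when PREPP lowers attributions and 7–24% when it lowers only 6-week crying, against 4–8% with 6-week crying added (300 trials per cell). Component paths of opposite sign can offset each other in that total, so a modest combined rate does not make the component paths trustworthy.

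**Stable fussiness is not enough.** A reader might infer that a stably fussy infant by itself produces the false pathway. It does not, because treatment is randomised: PREPP must also shift 6-week attributions, directly or through crying. That shift is, however, what Aim 3B hypothesises.

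**Aim 2B would expose the error.** If PREPP has no effect on crying, the comparison of crying by arm would usually show no reduction to explain. This stands for that scenario, so it cannot be said that the trial is likely to credit a crying reduction to attributions. It does not help where PREPP lowers crying by another route: crying then really falls, and attributions can still be credited wrongly in up to 36% of trials.

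**The plan already compares alternative pathways.** This is a partial safeguard. Reverse paths are not excluded, but none is specified, and the stated reason is same-visit measurement, not the lag from week 6 to week 16.

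**Six-week crying is post-randomisation.** This stands. PREPP teaches carrying and swaddling, and all its contacts fall at or before 6 weeks postpartum, so part of its effect may already be in 6-week crying. It belongs in the pathway model, not in a list of baseline covariates.

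**Aim 3 is mechanistic.** It lies outside the five primary outcomes of Aims 1 and 2, so the trial's main conclusions are not affected.

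**Conclusion.** The concern holds in a limited form. The Aim 3B model as listed leaves the path from 6-week attributions to week-16 crying confounded by 6-week crying, which the trial already records. If PREPP shifts 6-week attributions by the plan's own d = 0.54, false mediation through that path in the sole-mediator model is about 18% to 75–78% for assumed correlations of 0.3 to 0.5, and 4–5% once 6-week crying is included. If PREPP moves neither attributions nor crying at 6 weeks, the rate is near or below nominal. The correlations are assumptions, and the size scales with their product.

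A reader might also infer that adding 6-week crying to the listed model restores the error rate. It does not while week-16 attributions remain a directed predictor of week-16 crying, because measures taken at the same visit cannot separate mediation from reverse causation.

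**What to change.** Pre-specify a lagged model as the main Aim 3B test of the temporally earlier pathway:
- Regress week-16 fuss/cry on treatment, 6-week attributions and 6-week fuss/cry.
- Let both 6-week measures depend on treatment, with a free covariance between them.
- Do not use week-16 attributions or sensitivity as directed predictors of week-16 fuss/cry. Omit them, as in the reduced model of Aim 3A, or link them to it by residual covariances only.

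Report the current model with week-16 mediators as secondary, and state that it cannot separate mediation from reverse causation.

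The cost is SAP wording, with no new data. The downside is a narrower estimand: any PREPP or attribution effect already present in crying by week 6 is not counted, so the indirect effect is a conservative estimate for weeks 6 to 16, and the SAP should say so. This is a cheap improvement.

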#### **Prenatal Session 1 (28-32 weeks gestation)**

At this time point, if the individual agrees to participate in this session and gives consent, the individual is randomly assigned to one of two groups: Intervention vs. Enhanced Treatment As Usual (ETAU). When the participants are 28-32 weeks pregnant, they participate in an in-person session (pre-COVID) or in a virtual session (during COVID), either by phone or video call, and are asked to complete mood assessments, a cognitive assessments and answer questionnaires about feelings, life events, and sleep. Participants are asked a questionnaire about the effect of COVID-19 on their lives. In total, these questionnaires take about 90 minutes. All questionnaire results are entered in Redcap, an online secure database. All information entered in REDCap is de-identified using a screen ID. At home, we ask participants to wear an activity monitor for 7 full 24-hour days. We ask participants to complete a sleep diary noting sleep times and durations for the seven consecutive days they are wearing the activity monitor.

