### **Newborn Session (18-36 hours post-delivery)**

Participants are invited to have their newborn participate in an EEG sleep study that occurs between 18-36 hours after birth in the newborn nursery. We will examine variation in EEG left/right power asymmetry in relation to potential group differences in the effectiveness of the intervention in helping mothers function as a social "buffer" and modulate infant reactivity. The newborn EEG sleep protocol takes place in the newborn nursery while the baby is sleeping. This is a non-clinical EEG recording. A cap with EEG sensors is placed on the newborn's head by a trained member of the research team. The research team then waits for the baby to enter a state of quiet sleep. This allows the research team time to measure brain activity while the baby sleeps. The participant is reassured by the research team that although the sensors may leave a slight red mark for a brief time after they are removed, this procedure is completely painless and does not harm the newborn.

The EEG session takes approximately 30 minutes. This session is video recorded to allow the researchers to collect information about newborn behavior during the session. In total, including setup of materials and video-recording, the session is approximately 1.5 hours in duration.

The participant is allowed extra time to pick up, feed, comfort, or change the newborn to accommodate fussiness or discomfort at any time during the EEG. If the participant is uncomfortable with the EEG, they were free to stop the session.

If the participant gives birth prior to 37 weeks, they do not complete this EEG session with their newborn. The participant is still be able to proceed with the rest of the study. Participants did not complete this session during the COVID pandemic.

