### Treatment Protocols:

#### Experimental Arm: PREPP Intervention

The intervention is carried out at 5 timepoints, Session 1 at 28-32 gestational weeks, Session 2 at 34-39 gestational weeks, Session 3 at 6 weeks postpartum, Check-In Session 1 within 3 days of the birth and at Check 2 Session at 2 weeks postpartum. These sessions are scheduled to coincide with standard medical visits (3rd trimester ultrasounds and 6-Week Well Baby visit), which enable us to test the feasibility of incorporating these sessions into routine medical care. A licensed trained clinician or an unlicensed trained clinician under licensed supervision provide the intervention. The sessions of this preventive psychotherapy are comprised of three

components: (a) mindfulness and self-reflection skills, (b) parenting skills and (c)psycho-education. The intervention protocol encompasses the following 5 specific established behavioral techniques: (1) feeding the infant between 10 pm and midnight, even if s/he must be awakened ('a focal feed'); (2) accentuating differences between day and night cues so that there are higher levels of stimulation during the former than the latter; (3) assuming adequate weight gain is reached by 3 weeks, lengthening the latency to feeding time in the middle of the night by engaging in other attentive activities such as walking with the baby and diapering; the goal is to lengthen the nighttime feeding intervals by extinguishing the association between night time waking and feeding; (4) carrying infants for a minimum of 3 hours a day, throughout the day, independent of responding to crying, carrying during feeding, and whether the baby is awake; and (5) learning to swaddle the baby as a possible soothing intervention. Mindfulness-based tools are provided with the aim to (1) aid them to return to sleep after waking at night, (2) help them to cope better when their babies are distressed or unsoothable. These mindfulness exercises are provided as audio files via an App.

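### Aim 3C adjusts for newborn EEG as if it were a baseline, but it is recorded after randomisation and prenatal PREPP, so any treatment effect passing through it is removed from the mediated effect

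*Combined protocol and SAP*

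**What the plan says.** In the Statistical Analysis Plan (Analysis for Aim 3), Aim 3C is specified as "a mediation model with EEG power at week 6 and avg. infant sleep (actigraphy) quality will be assessed as mediators" of the treatment effect on week-16 maternal sleep, "controlling for EEG power at birth as a covariate".

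The timing of that covariate is set elsewhere in the protocol:

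- Randomisation takes place at Prenatal Session 1, at 28 to 32 weeks.
- The Experimental Arm section schedules PREPP as "Session 1 at 28-32 gestational weeks, Session 2 at 34-39 gestational weeks", followed by check-ins and a session after birth.
- The newborn recording "occurs between 18-36 hours after birth in the newborn nursery".

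On its purpose, the Newborn Session section says: "We will examine variation in EEG left/right power asymmetry in relation to potential group differences in the effectiveness of the intervention". The sentence goes on to mothers' role as a social buffer, and it is repeated for the week-6 EEG.

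On availability, the same section says: "If the participant gives birth prior to 37 weeks, they do not complete this EEG session with their newborn". It also says: "Participants did not complete this session during the COVID pandemic". The 6-Week Postpartum Session section offers EEG only when the visit is in person, and visits during COVID were virtual.

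The Power analysis section bases Aim 3 on 142 completers, then says that the full sample of 214 will enter the mediation models. No missing-data method is named for Aim 3, and no count of infants with either EEG is given.

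**The concern.** A covariate in a mediation model is harmless to the treatment-to-mediator path when treatment cannot have affected it. Newborn EEG does not meet that condition by design: it comes after randomisation and after the prenatal part of the intervention. Aim 2A, by contrast, adjusts its postpartum maternal outcomes for values taken in pregnancy.

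If PREPP works partly before birth, one route to the week-6 mediator is treatment to newborn EEG to week-6 EEG. Holding newborn EEG fixed closes that route. The reported indirect effect would then cover only what arises after birth, while the Aim 3C hypothesis concerns the whole effect of PREPP. The plan does not say that the narrower quantity is intended.

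A second issue is who is left in the model. Infants born before 37 weeks skip the newborn EEG but stay in the study, so they can have the mediator and lack the covariate. A complete-case fit would drop them, and so would select on term birth, itself a post-randomisation event.

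**Working it through.** **1. The plan's own figure.** Inputs from Power analysis: 214 randomised, 33% attrition, 142 completers, d = 0.54 and r = 0.26 on both paths, power above 80%.

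- Completers: 214 × (1 − 0.33) = 143.4, against 142 stated.
- Effect size: r = d/√(d² + 4) = 0.54/√4.2916 = 0.261.
- The alpha for Aim 3 is not stated; 0.05 two-sided is assumed. At N = 142, each path has power 0.890 (noncentral t), so joint significance has power 0.890² = 79%. A simulated bootstrap gives 76% (percentile) and 84% (bias-corrected).

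The stated figure is therefore reproduced to within the choice of method. At alpha 0.01 joint significance gives 52%, so the figure implies 0.05.

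**2. Effect of conditioning on newborn EEG.** Use standardised linear paths. Let a = 0.26 be the total path from treatment to week-6 EEG (the plan's r), a0 the path from treatment to newborn EEG, and s the path from newborn to week-6 EEG. Then

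- path left after adjustment = a − s × a0
- share of the EEG-mediated effect kept = 1 − s × a0/0.26.

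The documents give neither a0 nor s, so both are assumed over a range:

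| a0 | s = 0.3 | s = 0.5 | s = 0.7 |
|---|---|---|---|
| 0 | 100% | 100% | 100% |
| 0.05 | 94% | 90% | 87% |
| 0.15 | 83% | 71% | 60% |
| 0.26 | 70% | 50% | 30% |

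Example: s = 0.5 and a0 = 0.15 leave 0.26 − 0.075 = 0.185, and 0.185/0.26 = 71%. A simulation with n = 2,000,000 gave the same share: indirect effect 0.048 adjusted against 0.068 unadjusted. If a0 had the opposite sign to a, the formula gives more than 100%, so adjustment would then overstate the total.

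**3. Missing newborn EEG.** A dyad lost only because of the covariate must have a week-6 EEG but no newborn EEG. That means a preterm birth, a missed or declined nursery session, or a birth in the COVID period with an in-person week-6 visit. If this costs 10% (assumed), 142 falls to 128, and joint-significance power falls from 0.890² = 79% to 0.856² = 73% (at alpha 0.01, from 52% to 44%).

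Overall EEG availability is a separate matter. If 75%, 50% or 30% of the 142 have usable EEG (assumed), N is 107, 71 or 43 and power at alpha 0.05 is 62%, 37% or 17%. Most of that reduction would come from the mediator.

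**4. What omitting newborn EEG altogether would do.** Suppose newborn EEG also has a direct path g to maternal sleep. With a0 = 0, s = 0.5 and a true mediator-to-outcome path of 0.26, omission adds g × s/(1 − 0.26²) to that path:

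- g = 0.1: 0.05/0.932 = 0.054, about 21% too large.
- g = 0.2: 0.10/0.932 = 0.107, giving 0.37, about 41% too large.

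Here g and s are assumptions. With g = 0 there is no bias.

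**The case against.** The strongest reply is that nothing in the documents says PREPP changes newborn EEG power. The five infant-care techniques are applied after birth. The sentence about group differences names left/right asymmetry, not power, and it is boilerplate shared with the week-6 section. If PREPP leaves newborn EEG unchanged, adjustment removes nothing. This stands in part: the bias is conditional, and so is its direction. It does not make the covariate a baseline. A prenatal route through lower maternal distress, which is Aim 1, is open. Asymmetry is a contrast of left and right power, so a shift in one implies a shift in power on at least one side.

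A second reply is that newborn EEG may be a common cause of week-6 EEG and later sleep, so that controlling for it protects a path that randomisation does not. This stands, as step 4 shows, and it is why simply deleting the covariate is not the remedy.

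A reader might also infer that the covariate drops many infants and cuts Aim 3C power to roughly a third. The documents do not support that. They give no counts, and the week-6 EEG is itself limited to in-person visits, so most COVID-era dyads lack the mediator whatever is done about the covariate. Loss of dyads also presupposes complete-case fitting, which the plan does not specify.

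**Conclusion.** The structural point holds: Aim 3C conditions on a variable measured after randomisation and after prenatal treatment, and the protocol allows that this variable may relate to group. The resulting loss in the EEG-mediated effect is zero if prenatal PREPP does not move newborn EEG, and about 6% to 70% over the non-zero values tried. Those values are assumptions within a linear model without interactions. That the mediated effect is in fact understated cannot be concluded from the documents.

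The extra sample loss due to the covariate is real under complete-case fitting, but it cannot be quantified from the documents and is probably the smaller part of the EEG shortfall. The statement that all 214 will be used does need reconciling with EEG that is missing by design at both ages.

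Aim 3C is a mechanistic aim, and the five primary outcomes under Aims 1 and 2 are unaffected. The change is still worth making because it costs so little.

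**What to change.** In the structural equation model already planned:

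- Make newborn EEG an earlier mediator affected by treatment: treatment to newborn EEG to week-6 EEG to infant sleep and maternal sleep. Add direct paths from newborn EEG to the later mediators and to the outcome, so that it still controls mediator-outcome confounding.
- Report the total EEG-mediated effect, showing separately the part that passes through newborn EEG.
- Keep the covariate-adjusted model as a sensitivity analysis, labelled as the postnatal component only.
- Fit by full-information maximum likelihood and state the missing-at-random assumption it needs, given that absence depends on calendar period and preterm birth.
- Report the number with newborn EEG, with week-6 EEG and with both, by arm, and reconcile these with the statement that all 214 enter the mediation models.

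The cost is SAP wording, a few more parameters and slightly wider intervals. No new data are needed.
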